9.3. Prohibited Therapies

Since ecopipam and its metabolite (SCH40853) may inhibit CYP2D6, OATP1B1, PGP and UGT1A9, for any drug that is a substrate of these enzymes, the label for the drug should be consulted to decide if a dose adjustment is needed. Drugs that are strong inducers of these enzymes are prohibited. An illustrative list of such drugs is provided in the Prohibited Medications List in the Appendices.

Prohibited therapies per the exclusion criteria (Section 8.2) include medications which would have unfavorable interactions with ecopipam:

• Dopamine antagonists or agonists (including bupropion)

- Tetrabenazine
- Monoamine oxidase inhibitors
- St. John's Wort

9.4. Treatment Compliance

During the study period, subject compliance will be monitored by review of the tablet counts at the study site visits. Any violation of compliance will require evaluation by the Investigator and Sponsor to determine if the subject may continue the study.

9.5. Randomization and Blinding

No blinding will be needed as this is an open-label study.

10. STUDY DRUG MATERIALS AND MANAGEMENT

10.1. Study Drug

Ecopipam tablets

10.2. Study Drug Packaging and Labeling

Study drug will be supplied in labeled containers by the Sponsor. The product release certificates for ecopipam will be included in the clinical study report for this protocol. Any special storage conditions will be noted on the label and should be followed by the study site.

The labels will be produced by PCI Pharma Services. Minimally, the labels will contain the following information:

- 1. Name, address and telephone number of the Sponsor
- 2. Pharmaceutical dosage form, route of administration, quantity of dosage units, identifier, and dose strength
- 3. Lot number
- 4. Protocol Number
- 5. Study identifier
- 6. Study subject identification number
- 7. Directions of use
- 8. "Caution: New Drug Limited by Federal (US) law to investigational use (or equivalent for rest of world)"
- 9. "Keep out of reach of children"
- 10. Storage Conditions
- 11. Expiration Date

10.3. Study Drug Storage

Study drug must be stored as instructed on the study drug label. All relevant site-specific guidelines and country-specific labeling requirements must be followed. Study drug must be kept in a secure location and carefully stored at the study site within its original container and protected from light. A daily temperature log for monitoring of proper storage conditions must be maintained by the site.

10.4. Study Drug Preparation

Study drug will be prepared in 15 count bottles for ecopipam.

10.5. Administration

Ecopipam HCl will be supplied as 12.5-, 37,5-, 50-, 75-, and 100-mg tablets. The target dose is 2 mg/kg via oral administration.

During the 4-week titration period, the following ecopipam HCl doses will be administered for each of the weight bands:

- Those who weigh ≥18-≤23 kg will titrate from 12.5 mg daily to 37.5 mg daily: 12.5 mg during Week 1, 25 mg (two 12.5-mg tablets) during Week 2, and 37.5 mg during Weeks 3 and 4.
- Those who weigh >23- \leq 34 kg will titrate from 12.5 mg daily to 50 mg daily: 12.5 mg during Week 1, 25 mg (two 12.5-mg tablets) during Week 2, 37.5 mg during Week 3, and 50 mg during Week 4.
- Those who weigh >34- \leq 44 kg will titrate from 12.5 mg daily to 75 mg daily: 12.5 mg during Week 1, 25 mg (two 12.5-mg tablets) during Week 2, 50 mg during Week 3, and 75 mg during Week 4.
- Those who weigh >44- \leq 68 kg will titrate from 25 mg daily to 100 mg daily: 25 mg (two 12.5-mg tablets) during Week 1, 50 mg during Week 2, 75 mg during Week 3, and 100 mg during Week 4.
- Those who weigh >68- \leq 83 kg will titrate from 25 mg daily to 150 mg daily: 25 mg (two 12.5-mg tablets) during Week 1, 50 mg during Week 2, 100 mg during Week 3, and 150 mg (two 75-mg tablets) during Week 4.
- Those who weigh >83 kg will titrate from 25 mg daily to 200 mg daily: 25 mg (two 12.5-mg tablets) during Week 1, 50 mg during Week 2, 100 mg during Week 3, and 200 mg (two 100-mg tablets) during Week 4.

During the treatment phase, the following ecopipam HCl doses will be administered for each of the weight bands:

- Those who weigh $\ge 18 \le 23$ kg will receive 37.5 mg daily.
- Those who weigh >23-\(\le 34\) kg will receive 50 mg daily.
- Those who weigh >34-\(\le 44\) kg will receive 75 mg daily.
- Those who weigh >44-\(\le 68\) kg will receive 100 mg daily.
- Those who weigh >68-\le 83 kg will receive 150 mg daily.
- Those who weigh >83 kg will receive 200 mg daily.

All doses will be administered PO once daily in the evening.

At the end of the open-label treatment phase, subjects will titrate off therapy and receive ecopipam HCl doses that will be reduced by 25 mg/day until off of drug; signs of symptoms of withdrawal will be monitored.

Subjects with weight changes during the course of the study resulting in change in weight band may titrate to the dosing of the new weight band at the discretion of the Investigator and with the approval of the Medical Monitor. If approved, the dose of study medication should be increased according to the titration scheme noted for the new weight band.

10.6. Dosing Rationale

An ecopipam HCl dose of 2 mg/kg/day with titration is targeted in pediatric subjects \geq 6 to \leq 18 years of age at Baseline using the dosage regimen proposed in Table 4.

Table 4: Proposed Dosing Regimen

Weight (kg)	Dose (mg) Week 1	Dose (mg) Week 2	Dose (mg) Week 3	Dose (mg) Week 4 onwards
≥18 to ≤23	12.5	25 (2×12.5)	37.5	37.5
>23 to ≤34	12.5	25 (2×12.5)	37.5	50
>34 to ≤44	12.5	25 (2×12.5)	50	75
>44 to ≤68	25 (2×12.5)	50	75	100
>68 to ≤83	25 (2×12.5)	50	100	150 (2×75)
>83	25 (2×12.5)	50	100	200 (2×100)

This dosing regimen was chosen based on modeling and simulation with the results and important information summarized below:

- In a double-blind, placebo-controlled crossover study of 40 subjects with TS aged 7 to 17 years receiving ecopipam HCl at 50 mg (if <75 pounds) or 100 mg (if ≥75 pounds), after a titration, a post-hoc analysis showed that t ecopipam HCl likely has modest efficacy (Study PSY302);
- 2 mg/kg targets a mg/kg dose that is above the median mg/kg dose in 75% of subjects in Study PSY302, with the remaining 25% of subjects having a mg/kg dose that is substantially below the 95th percentile from Study PSY302;
- The predicted plasma concentration-time curves for the median, 5th percentile, and 95th percentile are within the exposures studied in PSY302, and similar to other proposed dosing regimens;
- The animal:human ratios for the active moieties (unconjugated parent plus active metabolite, SCH40853) are adequate based on the no-observed-adverse-effects-level (NOAEL) in the 3-month GLP toxicology study for mice (30 mg/kg), the 3-month GLP toxicology study in rhesus monkeys at 12 mg/kg, and the 1-year GLP toxicology study in cynomolgus monkeys at 12 mg/kg, and do not differ from those in Study PSY302 (Table 5).
- For rhesus and cynomolgus monkeys, the main toxicities observed at 12 mg/kg were decreased activity, decreased appetite, and decreased defecation. For cynomolgus monkeys, these AEs were reported during the first 1 to 3 weeks (hence, the need for titration in the proposed clinical study Protocol EBS-101-OL-001).
- In Study PSY302, the TEAEs were gastrointestinal disorders (e.g., nausea, upper abdominal pain), general disorders and administrative site conditions (e.g., decreased appetite, fatigue), and nervous systems disorders (e.g., somnolence, headache, sedation). The current study will incorporate a 2-week titration which has the potential to improve tolerability.

• While studying multiple dose levels is important in a Phase 2b study, a dose titration approach (instead of fixed 3-dose parallel design study) was chosen because the PSY302 study suggested that doses lower than ~1.4 mg/kg the 25th percentile would be unlikely to have substantial efficacy. The exposure between ~1.4 mg/kg and ~2 mg/kg would have significant overlap in exposure (i.e., they would not be distinctly different doses), doses higher than ~2 mg/kg may not be well tolerated, and doses higher than ~2 mg/kg would result in animal:human exposures significantly lower than 1.

Table 5: Animal:Human Exposure Ratios with the Proposed Dosage Regimen of Ecopipam HCl to 7 to 16 Year Olds

Week	PK	Mice: Human Ratio ^{b,c}	Rhesus Monkey: Human Ratio ^c		Cynomolgus Human	•
		30 mg/kg	3 mg/kg	12 mg/kg	3 mg/kg	12 mg/kg
Combine	ed AUC ^a (1	ng*hr/mL)				
1	146	17.2×	2.1×	5.9×	2.1×	10.6×
2	289	8.7×	1.1×	3.0×	1.1×	5.3×
Full Dose	535	4.7×	0.6×	1.6×	0.6×	2.9×
Combine	ed C _{max} a (n	ig/mL)				
1	17.1	16.9×	1.4×	3.4×	1.5×	8.7×
2	34.3	8.4×	0.7×	1.7×	0.8×	4.3×
Full Dose	62.6	4.6×°	0.4×	0.92×	0.4×	2.4×°

 $^{^{\}rm a}$ Animal: human ratios were calculated based on combined unconjugated parent ecopipam HCl plus active metabolite SCH40853 AUC and $C_{\rm max}$.

 $[^]b$ The ratios for rats at 6 mg/kg are not included due to the fact that the assay sensitivity was not adequate (LLOQ=0.5 μg/mL), the AUC was determined with ≤3 data points, and there were too few concentrations above the LLOQ to determine the C_{max}

^c Ratios were calculated using the predicted exposure in Study PSY302. These animal:human ratios did not differ in most cases for the full dose where the animal:human C_{max} ratios differed by 0.1 times where noted.

10.7. Study Drug Accountability

The Investigator (or pharmacist, as appropriate) must maintain records of the delivery of the study drug to the study site, the inventory at the site, use for each subject, and return of the study drug to a delegate of the Sponsor. Total study site accountability will be conducted at the end of the study and the Investigator must explain all discrepancies.

A Drug Dispensing Log must be kept current and should contain the following information:

- Identification (subject number and initials as required by local regulations) of subject to whom the study drug was dispensed
- The dates and lot numbers for the study drug dispensed
- Initial inventory on receipt of drug at the site
- Final inventory on completion of the study

All records and inventory must be available for inspection by the Clinical Research Associate (CRA).

Due to the COVID-19 pandemic, in some cases direct to patient shipments may be necessary. In this case, study medication may be transported to the subject by a third party vendor who has systems in place to protect patient privacy and data integrity. On close-out of the site, all used and unused investigational product must be shipped to the Emalex-designated location. The Drug Dispensing Log must be available for monitoring, auditing, or inspection.

10.8. Study Drug Handling and Disposal

Current ICH Good Clinical Practices (GCP) Guidelines require the Investigator to ensure that study drug deliveries from the Sponsor are received by a responsible person (e.g., pharmacist), and

- That such deliveries are recorded
- That study drug is handled and stored safely and properly
- That study drug is only dispensed to study subjects in accordance with the protocol
- That any unused study drug is returned to the Sponsor or standard procedures for the alternative disposition of unused study drug are followed.

11. ASSESSMENT OF EFFICACY

Assessments may be completed in locations other than study clinic and/or via remote administration due to restrictions as a consequence of the COVID-19 pandemic or other qualifying event.

11.1 Efficacy Assessments

The YGTSS, CGI-TS-S, and C&A-GTS-QOL will be assessed at Baseline, Months 1, 3, 6, 9 and 12. The CGI-TS-I will be assessed at Months 1, 3, 6, 9 and 12.

The YGTSS is a clinician-completed rating scale used to quantify overall tic severity as well as specific subdomains of tic number, frequency, duration, intensity, and complexity. Each of these subdomains is scored, on a 5-point scale, separately for motor and vocal tics and then summed across both motor and vocal tics to yield a tic severity score ranging from 0 to 50. The YGTSS also provides for an overall impairment rating (0 = "none" to 50 = "severe"). The YGTSS has demonstrated acceptable internal consistency, good interrater reliability, and acceptable convergent and divergent validity. Efficacy will be analyzed for both the YGTSS-TTS and Global YGTSS.

The CGI consists of 2 reliable and valid 7-item Likert scales used to assess severity and change in clinical symptoms. The scale ranges from 1 = "very much improved" to 7 = very much worse" for the CGI-TS-I. The CGI severity scale (CGI-TS-S) will be used at each study site visit and ranges from 1 = "not ill at all" to 7 = "among the most extremely ill."

Gilles de la Tourette Syndrome—Quality of Life Scale for Children and Adolescents (C&A-GTS-QOL) is a patient-reported health related quality of life measure developed for children and adolescents. Versions of the scale appropriate for subjects 6-12 years of age and 13-18 years of age will be provided. Subjects who turn 13 during the course of the study should continue to be assessed using the version of the scale initially administered.

12. ASSESSMENT OF SAFETY

12.1. Safety Parameters

Study Visits may be completed in locations other than clinic and/or via remote administration due to restrictions as a consequence of the COVID-19 pandemic or other qualifying event. Safety will be monitored throughout the study at all visits by repeated adverse event (AE) monitoring, vital signs, the Columbia-Suicide Severity Rating Scale (C-SSRS), the Abnormal Involuntary Movement Scale (AIMS), the Barnes Akathisia Rating Scale (BARS), the Pediatric Anxiety Rating Scale (PARS) and Children's Depression Rating Scale-Revised (CDRS-R). In addition to these assessments, at Baseline, Months 1, 3, 6, 9 and 12 safety will also be monitored by clinical and laboratory evaluations and electrocardiogram (ECG) monitoring. At the Follow Up visit, AE monitoring, the C-SSRS, clinical and laboratory evaluations and vital signs will be assessed. Laboratory evaluations will include hematology, chemistry, urine values and HbA1c. A Follow Up phone call will be conducted 30 days after the last dose of study medication to assess AEs. Additional assessments (all visits except the follow up visit) will include the AIMS, the BARS, the CDRS-R and the PARS. C-SSRS will also be assessed (all visits including the Follow Up visit).

The C-SSRS is a low burden (approximately 5 minutes for completion) instrument to assess both suicidal behavior and ideation. The scale is appropriate for subjects from age 6 through to an elderly population.

The AIMS records the occurrences of tardive dyskinesia (TD) in subjects receiving neuroleptic medications. The test is used to detect TD and to follow the severity over time.

Barnes Akathisia Rating Scale (BARS) scale to assess the severity of drug-induced akathisia. Objective and subjective items in the scale measure the level of subject's restlessness.

Children's Depression Rating Scale-Revised (CDRS-R) is a clinically validated rating scale designed to assess psychiatric signs and symptoms of depressions in children and adolescents.

Pediatric Anxiety Rating Scale (PARS) is a clinician-rated instrument for assessing the severity of anxiety symptoms associated with common anxiety disorders and generalized anxiety in children and adolescents.

Vital Signs:

Vital signs will be collected each clinic visit. They include heart rate, blood pressure, orthostatic blood pressure and heart rate (after being supine for 5 minutes and 3 minutes after standing), height and weight.

Clinical Laboratory Assessments:

The following clinical laboratory tests will be performed in a fasting state at Baseline, Months 1, 3, 6, 9 and 12:

Clinical Laboratory Tests

Category Parameters

Hematology Red blood cell count, hemoglobin,

hematocrit, platelets, and white blood cell count with differential (neutrophils, bands lymphocytes, monocytes, eosinophils,

basophils)

Chemistry

Electrolytes Sodium, potassium, chloride, bicarbonate

Liver function tests

Alkaline phosphatase, aspartate

aminotransferase (AST), alanine

aminotransferase (ALT), total bilirubin,

direct bilirubin

Renal function parameters Blood urea/blood urea nitrogen (BUN),

creatinine

Other Glucose, calcium, albumin, cholesterol,

triglycerides, phosphorus, lactate dehydrogenase (LDH), total protein,

globulin

Urinalysis Complete urinalysis includes color,

appearance, specific gravity, pH, protein,

glucose, ketones, and blood with microscopic examination for positive

protein or blood results

Pregnancy Test Urine test (for women of childbearing

potential only)

Special Parameters - Hemoglobin

A1c (HbA1c)

Contraception Guidelines:

As specified in the Inclusion Criteria (Section 8.1), adolescent females of childbearing potential who are sexually active and male subjects who are sexually active must use a highly effective form of contraception throughout the study and for 30 days after the last dose of study drug. See the Contraception Guidelines for additional information.

Subjects must be monitored for signs of study drug abuse, and withdrawal or dependence and if detected must be recorded as AEs.

12.2. Adverse and Serious Adverse Events

12.2.1. Definition of Adverse Events

An AE is defined as any untoward medical occurrence in a subject administered a study drug and which does not necessarily have a causal relationship with this treatment. An AE can therefore be any unfavorable and unintended sign (including an abnormal laboratory finding), symptom, or disease temporally associated with the use of a study drug, whether or not related to the study

drug. In clinical studies, an AE can include an undesirable medical condition occurring at any time, including baseline or washout periods, even if no study treatment has been administered.

An abnormality identified during a medical test (e.g., laboratory parameter, vital sign, ECG data, physical examination) should be defined as an AE only if the abnormality meets one of the following criteria:

- Induces clinical signs or symptoms
- Requires active intervention
- Requires interruption or discontinuation of study medication
- The abnormality or investigational value is clinically significant in the opinion of the Investigator

All AEs that occur after any subject has been screened, enrolled, before treatment, during treatment, or within 30 days following the cessation of treatment, whether or not they are related to the study, must be recorded on forms provided by the Sponsor or its representative.

12.2.1.1. Treatment-Emergent Adverse Event

A TEAE is the development of an undesirable medical condition or the deterioration of a pre-existing medical condition following or during exposure to a pharmaceutical product, whether or not considered casually related to the product.

12.2.1.2. Serious Adverse Event

An SAE is an AE occurring during any study phase (i.e., baseline, treatment, washout, or followup), and at any dose of the investigational product, comparator or placebo, that fulfils one or more of the following:

- It results in death
- It is immediately life-threatening
- It requires in-patient hospitalization or prolongation of existing hospitalization
- It results in persistent or significant disability or incapacity
- It results in a congenital abnormality or birth defect
- It is an important medical event that may jeopardize the subject or may require medical intervention to prevent one of the outcomes listed above.

All SAEs that occur after any subject has been enrolled, before treatment, during treatment, or within 30 days following the cessation of treatment, whether or not they are related to the study, must be recorded on forms provided by the Sponsor or its representative.

12.2.1.3. Other Adverse Event

Other AEs (OAEs) will be identified by the Drug Safety Physician and if applicable, also by the Clinical Study Team Physician, during the evaluation of safety data for the clinical study report. Significant AEs of particular clinical importance, other than SAEs and those AEs leading to discontinuation of the subject from the study, will be classified as OAEs. For each OAE, a

narrative may be written and included in the clinical study report. Adverse events of special interest (AESI) are listed in Section 13.2.1.

12.3. Relationship to Study Drug

An Investigator who is qualified in medicine must make the determination of relationship to the investigational product for each AE (Unrelated, Possibly Related, or Probably Related). The Investigator should decide whether, in his or her medical judgment, there is a reasonable possibility that the event may have been caused by the investigational product. If no valid reason exists for suggesting a relationship, then the AE should be classified as "Unrelated." If there is any valid reason, even if undetermined, for suspecting a possible cause-and-effect relationship between the investigational product and the occurrence of the AE, then the AE should be considered "Related."

If the relationship between the AE/SAE and the investigational product is determined to be "possible" or "probable", the event will be considered to be related to the investigational product for the purposes of expedited regulatory reporting.

12.4. Recording Adverse Events

Adverse events spontaneously reported by the subject and/or in response to an open question from the study personnel or revealed by observation will be recorded during the study at the investigational site. Clinically significant changes in laboratory values, blood pressure, and pulse rate need not be reported as AEs per the Investigator's judgement. However, abnormal values that constitute an SAE or lead to discontinuation of administration of study drug must be reported and recorded as an AE. Information about AEs and SAEs will be collected from the signing of the informed consent form until 30 days following the last dose of study drug. The S/AE term should be reported in standard medical terminology when possible. For each S/AE, the Investigator will evaluate and report the onset (date and time), resolution (date and time), intensity, causality, action taken, serious outcome (if applicable), and whether or not it caused the subject to discontinue the study/study treatment.

Intensity will be assessed according to the following scale:

- Mild (awareness of sign or symptom, but easily tolerated)
- Moderate (discomfort sufficient to cause interference with normal activities)
- Severe (incapacitating, with inability to perform normal activities)

It is important to distinguish between serious and severe AEs. Severity is a measure of intensity, whereas seriousness is defined by the criteria under Section 12.2.1.2. An AE of severe intensity may not be considered serious.

Should a pregnancy of a subject or partner occur, it must be reported and recorded on the Sponsor or its representatives' pregnancy form. Pregnancy in itself is not regarded as an AE unless there is a suspicion that the investigational product may have interfered with the effectiveness of a contraceptive medication. Reports of pregnancy must be submitted to Syneos Health Safety & Pharmacovigilance within one business day:

Email Address: [contact]

Fax no. Americas: [contact]

Fax no. Europe and ROW [name]

The outcome of all pregnancies (spontaneous miscarriage, elective termination, normal birth or congenital abnormality) must be followed up and documented even if the subject was discontinued from the study.

All reports of congenital abnormalities/birth defects are SAEs. Spontaneous miscarriages should also be reported and handled as SAEs. Elective abortions without complications should not be handled as AEs.

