13.2. Planned Analyses

13.2.1. Safety Analysis

Adverse Events:

AEs, which include clinical laboratory test variables, will be documented from the time of the first study medication administration from the open label study until the subject's study participation is complete (study discontinuation and up to 30-days follow-up). All AEs that occur after the first study medication application and up to 30 days after the subject's last study medication application will be considered TEAEs.

Each AE will be reported with severity (mild, moderate, severe), seriousness, duration, resolution, action taken, and its relationship with the study medication (related or not related).

Adverse events will be summarized using system organ classification (SOC) defined by Medical Dictionary for Regulatory Activities (MedDRA); the following AEs will be categorized as AESIs in this study (AEs fitting under these categories to be fully described in the SAP):

- Extrapyramidal reactions (i.e. tardive dyskinesia, akathisia)
- Metabolic changes (hyperglycemia/diabetes mellitus, dyslipidemia, weight gain)
- Orthostatic hypotension
- Suicidality
- Leukopenia, neutropenia, agranulocytosis

TEAEs and AESIs will be summarized by severity and by relationship to study medication. Serious TEAEs and TEAEs leading to study termination will be summarized separately.

Other Safety Assessments:

Laboratory values, vital signs, ECG, and physical examination will be summarized descriptively by visit.

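### Protocol 12.2.1 and 12.4 give different rules for recording clinically significant laboratory, blood-pressure and pulse changes as AEs, so TEAE counts depend on which section a site follows

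*Protocol*

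**What the plan says.** Protocol 12.2.1 sets the rule for test findings: "An abnormality identified during a medical test (e.g., laboratory parameter, vital sign, ECG data, physical examination) should be defined as an AE only if" at least one of four criteria is met. The criteria are that the finding causes signs or symptoms, "Requires active intervention", "Requires interruption or discontinuation of study medication", or "The abnormality or investigational value is clinically significant in the opinion of the Investigator". The section ends with a general duty: all AEs within the collection period "must be recorded on forms provided by the Sponsor or its representative". It makes no exception for laboratory values or vital signs.

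Protocol 12.4, on recording, says: "Clinically significant changes in laboratory values, blood pressure, and pulse rate need not be reported as AEs per the Investigator's judgement". It then sets the compulsory minimum: "abnormal values that constitute an SAE or lead to discontinuation of administration of study drug must be reported and recorded as an AE".

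Protocol 13.2.1 defines AESIs as categories of AEs and leaves their full description to the SAP. Its five categories include "Metabolic changes (hyperglycemia/diabetes mellitus, dyslipidemia, weight gain"), orthostatic hypotension, and leukopenia/neutropenia/agranulocytosis. SAP 9.3 tabulates AESIs by system organ class and preferred term from coded AEs. Its ecopipam list keeps dyslipidaemia, hepatic disorders and hyperglycaemia/new-onset diabetes. Neither SAP list contains orthostatic hypotension, leukopenia/neutropenia or weight gain.

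**The concern.** The two sections start from the same judgement and reach different duties. In 12.2.1, the Investigator's view that a value is clinically significant is what makes it an AE. In 12.4, changes already called clinically significant are left to discretion. A site can follow either section and be compliant.

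Long-term safety and tolerability is the primary objective, and the AE and AESI tables contain only what sites record. There is no concurrent control arm in which under-recording would show up as an implausible rate. Protocol 5.3.2 names lipid changes, hyperglycaemia and orthostatic hypotension as areas of possible advantage. Protocol 5.3.1 concedes that earlier glucose and lipid shift data were absent from the previous brochure, that orthostatic data were not documented, and that reassurance came from adverse event tables. If the tables in this study are also incomplete for such findings, that gap is only partly closed.

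**Working it through.** No arithmetic applies, because the plan states no rate, sample size or event count on this point. The check sets the two rules side by side for a laboratory, blood-pressure or pulse abnormality.

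| Finding | Protocol 12.2.1 | Protocol 12.4 |
|---|---|---|
| Is an SAE | Record | Record |
| Leads to discontinuation of drug | Record | Record |
| Interrupts drug, later restarted | Record | Not compulsory on a plain reading |
| Needs active intervention | Record | Not compulsory |
| Causes signs or symptoms | Record | Symptom recorded if reported or observed; the abnormal value itself not compulsory |
| Clinically significant only | Record | Optional |

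**Where the rules part.** They agree on the first two rows. They differ clearly on the last row and, in whole or part, on the three between.

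**From recording to tables.** SAP 9.3 builds the TEAE and AESI tables from recorded, coded AEs and gives no rule that turns a measured value into an AE or AESI. An unrecorded finding is absent from every AE table.

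**Bounds.** Let N be the number of non-serious, non-discontinuing findings that meet a 12.2.1 criterion. Full use of 12.2.1 records N. Use of 12.4 records some number between 0 and N. The undercount therefore lies between 0 and N and cannot be negative. The documents give neither N nor the share of sites using each rule.

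**Which tables.**
- *SAP AESI tables:* of the groups in the ecopipam list, those resting mainly on laboratory values are dyslipidaemia, hyperglycaemia/diabetes and hepatic disorders.
- *General TEAE tables:* blood-pressure and neutrophil findings can be lost here.
- *Weight, ECG and examination findings:* these are not named in the 12.4 exception and stay under 12.2.1.

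**What survives without an AE record.**
- SAP 9.4 gives low/normal/high shift tables by visit for haematology, biochemistry, urinalysis and HbA1c, with banded shifts for HbA1c and total cholesterol.
- SAP 9.5 summarises supine and standing blood pressure and their changes from baseline, and applies outlier rules to heart rate.
- SAP 9.5 derives no supine-to-standing drop and sets no blood-pressure threshold, so no planned table counts subjects with an orthostatic fall from the measurements.
- None of these tables shows whether a finding was judged clinically significant, was treated, or interrupted dosing.

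**The case against.** The best defence is that 12.4 permits omission but does not forbid recording, so a careful Investigator can satisfy both sections. That is true, and it is why the loss may be nil. It does not reconcile the sections, because an optional entry and a compulsory one are different rules.

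The wording of 12.2.1 can also be read as giving necessary rather than sufficient conditions. However, the general AE definition in that section already covers abnormal laboratory findings, and the recording duty follows without an exception. The statement in 13.2.1 that AEs include laboratory variables adds little, since it sets no recording threshold.

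Three mitigating points stand:
- Protocol 9.2 asks for an AE entry when a concomitant medication was given for that AE, which supports recording medically treated abnormalities.
- The first sentence of 12.4 captures complaints and observed events, so symptomatic orthostatic hypotension should be recorded.
- Protocol 7.5 and 8.3 use discontinuation for a stop after which dosing may restart, so the interruption row is arguable.

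A reader might infer that three of the protocol's five AESI categories lose counts because of 12.4. The SAP does not support this. Orthostatic hypotension, leukopenia/neutropenia and weight gain are missing from its AESI lists whichever section a site follows, and weight is outside the 12.4 exception.

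A reader might also put a figure on the loss. If true incidence were 10% and half the sites recorded nothing, the recorded rate would be 10% × (1 − 0.5) = 5%. Both inputs are assumptions. Total non-recording is also a worst case, because 12.4 still compels SAEs and discontinuations and permits the rest.

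**Conclusion.** The inconsistency is real and lies in the current protocol text. For non-serious laboratory, blood-pressure and pulse findings that do not lead to discontinuation, the two sections give different recording duties, and the effect on TEAE counts can only be downward. Its size cannot be determined from the documents: it ranges from none to all such findings.

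Under the SAP as written, site-dependent AESI loss falls mainly on dyslipidaemia, hyperglycaemia/diabetes and hepatic disorders. Blood-pressure and neutrophil findings are at risk in the general TEAE tables.

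The documents do not support the inference that these safety signals would be invisible. Measured values are summarised and listed regardless of AE recording, so what is at risk is the count of recorded events. The protection is weakest for orthostatic blood pressure. The conclusion assumes only that some sites may use the discretion 12.4 gives them.

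**What to change.** **Protocol.** Reconcile the sections by replacing two sentences in 12.4, the one on clinically significant changes and the one that follows it, with a cross-reference. Suggested text: *Abnormal laboratory, vital-sign, ECG or examination findings are recorded as AEs whenever they meet any criterion in Section 12.2.1.*

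**SAP.** Add a by-subject listing that derives threshold-based laboratory and orthostatic blood-pressure abnormalities from the measured values and shows those with no matching AE. The sponsor should set the thresholds. The listing should not depend on a clinical-significance flag: the documents show one only for the overall ECG result (SAP 9.6).

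**If the data are already locked.** SAP Section 10 records updates made after database lock, so rewording 12.4 may not recover what was not recorded. In that case, run the listing on the existing data and disclose the conflicting instructions wherever AE and AESI rates are reported.

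**Cost.** One paragraph of protocol text with a note to sites, and one extra listing. Recorded AE rates may rise, and rates before and after a mid-study change would not be strictly comparable.
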